## 6.6. Laboratory investigations

A portion of the blood sample will be used for a full blood count, and will be examined for malaria by thick and thin film, and for *Mansonella perstans* infection using a modified Knott's method. Individuals found to have positive results for malaria will be treated according to government guidelines (currently with artemether combination therapy as first line), whether or not they are symptomatic. Lipid profiles (Cholesterol, High Density Lipids (HLD), Low Density Lipids (LDL) and Triglycerides) will be measured using the homogeneous enzymatic colorimetric assay.

The remaining blood will be aliquoted into labelled microtubes and stored at  $-80^{\circ}\text{C}$  for later measurement for HbA1c using Turbidimetric inhibition immunoassay. Plasma/serum will be stored for later measurement of CRP.

6.7. Plasma/serum and urine will also be stored for metabolomics. Metabolomics involves the measurement and profiling of small molecules that can reflect the metabolic response at the cellular, tissue and organ level and can provide us with further insight into the functioning and induction of the immune response. Metabolomic studies in infection models have revealed novel insight into how lipid related metabolites can play an important role in viral (53) and bacterial (54) infections. Importantly, exciting work has shown that the metabolic state of immune cells can have far reaching consequences for the development of long term memory response (55). Of particular relevance to this project, there is also evidence that helminth infections can influence immune responses and inflammation through production of small molecules such as short chain fatty acids (acetate, proprionate and butyrate), which have immunomodulating properties (56, 57). Therefore, whole metabolome measurements will be made in urine and serum and both untargeted and pathway specific analysis will be applied to identify metabolic profiles related to infectious exposure and CVD risk factors. This work will be conducted in collaboration with colleagues at the Leiden University Medical Centre, the Netherlands, where suitable equipment and expertise is available. A further protocol amendment with details of the methods to be used and analyses to be conducted, and a material transfer agreement, will be submitted when funding for this work has been secured. Sample size determination

The sample size is determined by the number of children still under follow-up within the cohort. We are aiming to see at least 1000 children. This will give considerable power to detect effects even of quite

rare exposures on the primary outcome, blood pressure. For example, assuming 8% were low birth weight (47) and that the standard deviation among children aged 10 years is 12 mmHg for systolic blood pressure and 8 mmHg for diastolic blood pressure (as in our recent pilot study in schools – unpublished data) this study will have over 80% power, with  $p=0.05$ , to detect an elevation of systolic blood pressure of 4 mm Hg and nearly 90% power to detect and elevation of diastolic blood pressure among low birth weight children of 3 mmHg. However using birth weight as a continuous explanatory variable will give greater power to detect effect on blood pressure than dichotomising birth weight (58).

A cohort of 1000 infants with the same measured variability in blood pressure would have 80 % power to detect an associated genetic variant with a mean allele frequency of 10 % producing a change in blood pressure of 4 mmHg to a GWAS level of significance ( $5 \times 10^{-8}$ ) using an additive mode of inheritance (calculated using the QUANTO software: <http://hydra.usc.edu/gxe>). Even if GWAS significant associations are not found within this cohort, it would be possible to use findings both from previously published work (59) and unpublished work from the Kyamulibwa analyses to model contributions of genetic variants and other measured variables on the blood pressure outcome (60).

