### 6.2. Study area and participants

This study will be conducted among the current EMaBS participants. Briefly, the EMABS is located on the Entebbe peninsula in Uganda, an area occupied by peri-urban, rural, and fishing communities. In total, 2507 pregnant women were enrolled and 2345 live births were recorded (46, 47). There are 1964 (82 %) children for whom birth weight is available (46) and 1622 (69%) children were seen at age 5 years (48). We continue to see over 1000 children for routine follow up visits per year.

Children aged 10 or 11 years of age who are currently under follow up in the EMaBS birth cohort will be invited to enrol into this study. They will be included in the study at routine annual visits if they are well, in the opinion of the study physician and if written, informed consent is provided by the parent or guardian, and written, informed assent is provided by the child. Children who are unwell will be treated for current illness and invited to return for the blood pressure assessment when they have recovered. Children will be excluded from this assessment if consent and assent for it are not given.

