## 6.4. Exposures

6.4.1. Birth weight (grams) will be the main exposure

Other exposures considered will include the following:

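### The power example for birth weight needs 1000 children with a recorded birth weight, but the target is 1000 children seen, with no allowance for the missing birth weights that the protocol reports

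*Protocol*

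**What the plan says.** Section 6.4.1 of the protocol states: "Birth weight (grams) will be the main exposure". Objective 5.1.1 is its association with blood pressure at age 10 to 11.

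The sample size text (6.7 in the contents list) says the number is set by the children still under follow-up: "We are aiming to see at least 1000 children". As an example it assumes that 8% are of low birth weight and that the standard deviation "is 12 mmHg for systolic blood pressure and 8 mmHg for diastolic blood pressure". It then says "this study will have over 80% power", at p=0.05, "to detect an elevation of systolic blood pressure of 4 mm Hg and nearly 90% power to detect and elevation of diastolic blood pressure", the diastolic difference being 3 mmHg among low-birth-weight children. It adds that birth weight used as a continuous variable will have greater power, without a figure.

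Section 6.2 says, directly after giving 2345 live births: "There are 1964 (82 %) children for whom birth weight is available". It reports 1622 children (69%) seen at age 5 and over 1000 seen each year for routine visits. Entry requires age 10 or 11, active follow-up, being well, consent and assent. It does not require a recorded birth weight.

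**The concern.** A child with no recorded birth weight adds nothing to an observed-data analysis of birth weight and blood pressure. The power example nevertheless uses the number of children to be seen, not the number expected to have both birth weight and blood pressure. The same document shows that birth weight is missing for part of the cohort.

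These two examples are the only quantified power claims for the main exposure, and the systolic one has little room: it is 81.6% on its own inputs. A modest shortfall in recorded birth weights takes it under the 80% claimed. A reader who relies on the statement would then think the low-birth-weight comparison more sensitive than it is.

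**Working it through.** **Inputs.** From the sample size text: n = 1000; low-birth-weight share 0.08; SD 12 mmHg systolic and 8 mmHg diastolic; differences 4 and 3 mmHg; p = 0.05. Sidedness is not stated; two-sided is used here. From section 6.2: 1964 children with a birth weight, printed as 82%; 2345 live births.

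**Formulae** (normal approximation):

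SE = SD / √(n × 0.08 × 0.92)

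power = Φ(difference / SE − 1.96)

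difference detectable with 80% power = (1.960 + 0.842) × SE

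**Step 1: reproduce the stated figures.** With n = 1000 (80 against 920), the systolic SE is 12/√73.6 = 1.399. So 4/1.399 = 2.86 and power is 81.6%. The diastolic SE is 8/√73.6 = 0.933. So 3/0.933 = 3.22 and power is 89.6%. The noncentral t gives 81.5% and 89.5%. These match the claims. A one-sided test would give 88.8% and 94.2%, and the second does not fit a claim of nearly 90%. The stated powers therefore rest on 1000 children who all have a birth weight.

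**Step 2: availability.** 1964/2345 = 83.8%, not 82%. The neighbouring figure, 1622/2345 = 69.2%, agrees with its printed 69%, so live births look like the intended denominator. The 82% would need a denominator of about 1964/0.82 = 2395, which is neither the live births (2345) nor the women enrolled (2507).

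**Step 3: apply availability to 1000 children seen.** The share among attenders is not given, so a range is shown. The 90% row is an assumption for illustration.

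| Availability | n analysed | Systolic power | Diastolic power | Detectable with 80% power (sys / dia, mmHg) |
|---|---|---|---|---|
| 100% | 1000 | 81.6% | 89.6% | 3.9 / 2.6 |
| 90% (assumed) | 900 | 77% | 86% | 4.1 / 2.8 |
| 83.8% | 838 | 74.5% | 83.8% | 4.3 / 2.9 |
| 82% | 820 | 73.6% | 83.0% | 4.3 / 2.9 |

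For example, at n = 820 the systolic SE is 12/√(820 × 0.0736) = 1.545. So 4/1.545 = 2.59 and power is Φ(0.63), about 73.6%.

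**Step 4: the break-even point.** The n for 80% systolic power is (2.802 × 12/4)² / 0.0736 = about 960 (963 if the low-birth-weight group is rounded up to 77 whole children). That is about 96% completeness among 1000 seen. Alternatively it is about 960/0.838 = 1146 to 960/0.82 = 1171 children seen, or roughly 1150 to 1170. Diastolic power stays above 80% throughout the table but is no longer nearly 90% in the last two rows.

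**Step 5: the continuous analysis.** Assume normally distributed birth weight, a linear relation and low birth weight as the lowest 8%. The two groups then differ by about 2.02 SD of birth weight, so a 4 mmHg contrast corresponds to 4/2.02 = 1.98 mmHg per SD. At n = 820 the SE per SD is 12/√820 = 0.42 and power is about 99.7%. The contrast detectable with 80% power is about 2.802 × 0.42 × 2.02 = 2.4 mmHg systolic, and about 1.6 mmHg diastolic.

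**The case against.** Four points can be made in the plan's defence.

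First, the 82% describes the whole birth cohort, not the children still followed at 10 to 11 years. The 1964 children with a birth weight outnumber the 1000 to be seen, so completeness among attenders could be higher or lower than 82–84%. This stands. A reader might infer that the protocol says only 82% of the study children have a birth weight, and that the true systolic power is therefore 73–74%. The document does not say so.

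Second, 1000 is a minimum. Section 6.2 has over 1000 children seen each year, and section 6.3.1 plans for all active participants to be seen within two years. About 1150 to 1170 children seen would restore 80% systolic power at the cohort's availability. This stands as a possibility, but the protocol commits to no such number.

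Third, the calculation is offered as an example, and the planned analysis uses birth weight in grams. Step 5 shows that, under a linear relation, that analysis would exceed the stated power even with 18% of birth weights missing. This largely removes the stronger inference that a null birth-weight result would be over-interpreted for want of power. It depends on linearity; an effect confined to low-birth-weight children would behave differently.

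Fourth, the arithmetic is correct on its inputs. That is so. The fault is in the number of children put into it, and the protocol neither states nor justifies complete birth weights.

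**Conclusion.** The concern holds in a conditional form. The example counts every one of the 1000 children seen as having a birth weight, although the protocol itself reports missing birth weights and does not make a recorded one a condition of entry. If the cohort's availability applies to attenders and exactly 1000 are seen, power is about 74% for 4 mmHg systolic and 83–84% for 3 mmHg diastolic. These are not a proven replacement for the stated powers. What does not depend on the exact availability is the narrow margin: on the protocol's own inputs, the systolic claim fails as soon as fewer than about 960 children have a birth weight.

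Severity is moderate. The point affects the dichotomised example, not the validity of the study, and the document does not support reading it as an underpowered primary objective. Separately, the printed 82% does not match 1964 out of 2345.

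**What to change.** - Count the active cohort children with a recorded birth weight. These data were collected at birth, so the number should be obtainable now. If it is not, state the completeness assumed.
- Restate the power, or the differences detectable with 80% power, on that number. If 820 to 838 prove analysable, that means about 74% for 4 mmHg systolic, 83–84% for 3 mmHg diastolic, and detectable differences of about 4.3 and 2.9 mmHg.
- Add a precision or power figure for the continuous birth-weight analysis, with the birth-weight SD labelled as an assumption. The protocol gives none. As an illustration, an SD of 500 g and n = 838 give a systolic slope SE of 12/(0.5 × √838) = 0.83 mmHg per kg, and a slope detectable with 80% power of about 2.3 mmHg per kg.
- In section 6.2, correct 82% to 84% or state the denominator used.

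The cost is a simple count and a few lines of protocol wording. Recruitment, eligibility and analysis do not change; the quoted power may become somewhat less favourable.

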## 6.8. Ethical considerations

The influence of birth weight on blood pressure among African children is still unknown and this is what this study will investigate.

Blood pressure assessment carries no risk to the child and causes only very minor discomfort. Obtaining a blood sample causes minor discomfort. The participants will be informed of the results of their blood pressure assessment, and of results from the blood tests as they become available. This is likely to have health benefits, including education about high blood pressure for those with normal findings, and education, provision of investigation, and advice and assistance with management for those found to be affected. Treatment will be offered, if required, up to the end of our current funding period (expected to be August 2016). Affected children and their parents or guardians will be referred for further management at Entebbe Hospital if follow up at the EMaBS clinic is not possible thereafter. Entebbe Hospital Staff will be offered continuing medical education on the management of high blood pressure in children to enable them to take this on.

Genetic data are already available for children in EMaBS, based on approval previously given for protocol Appendix 14. The informed consent process for this study will include an explanation that we now propose to use the genetic data and available DNA to examine associations with blood pressure.

Collected data will be securely and confidentially kept by the statistician/ data manager.

EMaBS children each have a unique identifier which is used at all study visits and on all data collection forms. The unique identifier, unavoidably, has the potential to allow data to be linked to an individual child. The unique identifier will be used to create the required, merged data sets for this analysis. These will include socio-demographic and clinical data from the current, and previous, study visits, laboratory data on infections, laboratory data on CVD biomarkers and genetic data. Data shared between collaborators in the study will be anonymised. Genetic data made available in open access, on-line databases will have all identifiers removed.

Both written informed consent and assent will be obtained for each child's participation in the additional blood pressure study procedures, and for the additional genetic analyses. Ethical approval will be sought from the ethics committees the Uganda Virus research Institute Ethics committee and the Uganda National Council for Science and Technology.

## 6.9. Data management

### 6.9.1. Data entry and quality assurance

Data will be collected on standardised clinical record forms (CRFs) by trained nurses, clinician and laboratory personnel. Sample identification data will be recorded on these forms at the time of sample collection, and results will be added at the laboratory. Completed CRFs will be collated and batched by the research teams or the Study Clerk, and then sent to the MRC/UVRI statistics section for double data entry and verification by data entrants.

The statistician / data manager will review entered data and generate queries at regular intervals which will be addressed by field, clinic or laboratory staff. Necessary corrections will be made. Data entry and data management will be overseen by a statistician/data manager at the MRC Unit. Data will be maintained on the MRC Unit server and backed up using standard Unit procedures.

Genetic data will be generated and analysed predominantly in the laboratories of the collaborating institutions: Oxford and the Sanger Institute. Plans are in place to develop sufficient infrastructure to

perform complex genetic analyses, such as those proposed herein, within Entebbe, Uganda. Blanket consent for genetic analyses related to infectious and inflammatory disease has already been approved and acquired using the EMaBS amendment 13. The re-analysis of the genetic data with respect to hypertension and other related cardiovascular disease will be stressed to the participant during the consenting process for this new study. Again, in line with the EMaBS amendment 13 and recent guidelines released by the European Society of Human Genetics (61). If any deleterious variants are identified and validated in any participant, every effort will be made to re-contact the individual concerned and provide appropriate ethical counselling. Such steps would only be taken after close consultation with experts in clinical genetics at the collaborating genetic institutions and following any additional guidelines that may be in place at the time. Such re-contacting would be facilitated by the excellent network in place as part of the on-going EMaBS. All resultant data will also be deposited in international repositories such as the European Bioinformatics Institute in Hinxton, UK in keeping with routine procedures and the previous ethical approval of genetic analyses undertaken for EMaBS. Any such storage will be anonymised using different identifying codes to those used within EMaBS.

#### 6.9.2. Analysis plan

For each study objective, the analysis plan has been set out. Prior to each analysis, a list of all variables to be considered will be prepared.

##### **6.9.2.1. To determine whether there is an association between birth weight and blood pressure among 10 and 11 year old children in EMaBS.**

Blood pressure will be treated as a continuous variable. We will conduct univariable analyses to assess the relationship between birth weight and blood pressure. We will fit multiple regression models of blood pressure separately for systolic and diastolic, on birth weight and appropriate potential confounders.

##### **6.9.2.2. To identify other early life exposures associated with blood pressure among 10 and 11 year old children in EMaBS.**

Univariable analyses for early life exposures in utero and early life will be conducted. We will fit multiple regression models of blood pressure separately for systolic and diastolic pressure on early life exposures and appropriate potential confounders.

We will develop a conceptual framework describing anticipated relationships between the exposures that we have assessed. Based on these, univariable and multivariable analyses models will be fitted to assess the relationships between the main exposures, the potential confounders, and the primary and secondary outcomes.

**6.9.2.3. To investigate whether the same exposures are associated with metabolic parameters among 10 and 11 year old children in EMaBS.**

Univariate and multiple regression models will be fitted for each metabolic parameter (HbA1c, HDL and total cholesterol) on potential risk factors and confounders.

**6.9.2.4. To investigate whether genetic polymorphisms are associated with blood pressure and biomarkers of CVD risk among 10 and 11 year old children in EMaBS.**

Genome-wide genotype data at 2.5 million variant sites will be available for a large proportion of the EMaBS children through the prior-approved GWAS study. As part of the original analysis the data will have already undergone significant quality control procedures including exclusion of individuals based on low call rates and high rates of heterozygosity, and genotyped SNPs will have been excluded based on high rates of missingness and heterozygosity and deviation from Hardy-Weinberg equilibrium. Each genetic variant will be tested for association with blood pressure both as a quantitative and binary variable using linear or logistic regression accounting for the measured covariates discussed above. Ethnicity will be controlled for using a mixed model (GEMMA) analysis or similar. If no significant associations are identified, then established methods will be used to test for contribution of recognised associated variants in the development of pathological hypertension using established methodology (60).

Furthermore, a range of other analyses will be possible using the existing data and material. For example, it will be possible to test for association of variants within genes such as ApoL1 using a gene association method of analysis or it may be possible to identify variants associated with the development of extreme phenotypes of hypertension using either the existing genotype data or next-generation sequencing techniques such as exome or whole-genome sequencing which are planned for the existing EMaBS cohort genetic studies.

## **7. Quality assurance and audit**

To ensure quality and reliability of the data of this study SOPs will be developed for clinic and laboratory procedures. The study will be regular monitored and conducted in accordance to the principles of GCP/GCLP.

## **8. Potential limitations; anticipated problems**

Some data of interest have not yet been collected, such as paternal details in relation to hypertension, such as family history, which may be important. It will only be possible to collect this information from children who are still under follow up (and even for some of those under follow up, information about their parents may be lacking). For mothers, blood pressure reading at enrolment during pregnancy is available, as well as history of hypertension in the mother's family.

## **9. Significance of the proposed work**

This will be the first study in Uganda, and one of the first in the region, to investigate whether birth weight and pre- and peri-natal exposures are important in programming blood pressure among African children. The existence of this long standing birth cohort in Entebbe is a unique opportunity to investigate factors associated with blood pressure programming in an African setting. The study will provide data on important exposures associated with high blood pressure in children. This will be important in developing strategies for prevention of hypertension and cardiovascular disease in this setting.

## **10. Distribution of responsibilities**

The Principal Investigator will be responsible for overseeing all aspects of the study. The Study team will consist of the Principal Investigator, other co-investigators, the study physicians, clinical and laboratory staff, as well as field workers/ interviewer who will regularly meet to discuss any study related issues, including medical and administrative issues. The Principal Investigator and project leader will prepare and submit annual progress reports to ethics committees.

